## 7.2 OPTIONAL SUB-STUDY PROCEDURES

For patients who provide consent for the optional sub-study the following additional procedure will be completed after providing consent to the optional sub-study and prior to the first PROSTVAC treatment.

- TSST: 70 minute stress test that includes saliva samples, blood pressure and heart rate monitoring and subjective units of distress (SUD) scale. More information about the TSST procedures is outlined in Section 8.

## 7.3 OFF-STUDY ASSESSMENTS

Off study assessments will consist of those procedures indicated for day 730 if the patient's participation ends at that time, or at any earlier time. These include:

- clinical examination (history and physical examination);
- assessment of toxicity or adverse events;
- CBCD;
- CMP
- bone scan and CT scan of abdomen, and pelvis (a Prostascint scan or MRI of abdomen, pelvis can be substituted). Scans will not be repeated at the off-study point if they have been performed in the preceding 2 months.
- PSA;

- total testosterone;
- research assessments
  - Blood samples-See Section 8 for details
  - Quality of Life questionnaires

## 7.4 SAFETY ASSESSMENTS

Safety assessments will be performed continuously throughout the entire study, and will occur at every clinic visit, as indicated in [Appendix A](#). At the minimum assessments will include a complete history and physical examination, and the following laboratory studies: CBCD, CMP, and testosterone.

Toxicities will be defined by the CTCAE v 4.0.

## 7.5 EFFICACY ASSESSMENTS

Efficacy assessments will primarily be performed by measurement of PSA and by physical assessment. Imaging studies (CT scans of the abdomen and pelvis, and bone scans) will be performed at baseline (up to 16 weeks prior to treatment) and at the end of the study (or within the preceding 2 months before end of study). Otherwise, scans will be performed only if clinically indicated for evaluation of relapse or off study. Additional forms of imaging (Prostascint scan, MRI) may be substituted for a CT scan of the abdomen and pelvis if clinically indicated. However, the imaging method used at baseline will be used for follow up scans. Compliance with therapy may be considered a component of the efficacy assessment. Compliance with PROSTVAC-V/F will be monitored at each visit by interviewing the patient and reviewing the infusion center records for administration.

Both primary and secondary efficacy assessment involve measurement of RFS. Recurrence will be defined as the occurrence of any of the following:

- Institution of new prostate cancer therapy
- First detection of a PSA level  $\geq 0.2$  ng/mL (confirmed  $> 30$  days later) after completion of all PROSTVAC V/F vaccine doses
- Development of radiographically-demonstrable metastases
- Death

RFS at two years will be met if a patient has met none of the above criteria two years post-surgery. RFS as a time to event endpoint will be measured as the time in days from surgery to any of the above conditions being met.

### 7.5.1 Primary Efficacy Assessment

The primary study endpoint is recurrence-free status at 2 years after prostatectomy. RFS will be defined as in Section 10.2. Observed probability of RFS will be compared with the same parameter obtained from similar historical patient series.

### 7.5.2 Secondary Efficacy Assessments

The secondary efficacy assessment will consist of a comparison of the observed RFS values with predicted RFS values calculated for the enrolled subjects by the Duke and CaPSURE algorithms.

The RFS values will be plotted using Kaplan-Meier methods, and the observed and predicted RFS values will be compared using the logrank test.

## 8 CORRELATIVE STUDIES

### 8.1 RESEARCH BLOOD COLLECTIONS

A variety of analyses will be performed on the research blood samples collected for this study. To evaluate biological responses to vaccinations, plasma, serum, as well as whole blood samples will be collected from all enrolled subjects. Plasma will be analyzed for the development of antibodies to the vaccinia and fowlpox virus vectors, the PSA insert, other prostate specific antigens, as well as tumor associated antigens. Serum will also be profiled for changes in cytokine and chemokine expression and circulating tumor markers. Immune function analysis will be performed by isolation of PBMCs for immune function assays. PBMCs will be evaluated for PSA antigen-specific responses by ELISPOT and flow cytometric-based methods. Determinant spreading to other prostate antigens and tumor-associated antigens will also be examined. All evaluations will be performed at laboratories using standardized procedures. Subject samples may be kept for up to one year past the end of the trial for assay development, implementation, and data review. These described analyses will generate a large dataset that will potentially enable the identification of new biomarkers of disease prognosis and/or vaccine response.

Research assessments will not be made in real time, since they will require analyses that will be performed only in “batch mode” when samples are available. Research samples will be collected as indicated and stored for future assays, in accordance with MUSC and VAMC policies.

All patients will be expected to provide blood for research purposes per the timepoints outlined within the study calendar (Appendix A). Each research blood collection will require 38mL of anticoagulated peripheral whole blood.

Research Blood Collection Timepoints	At each blood collection, collect the following	
	Amount of Blood	Tube type
Baseline Day 85 Day 225 Day 730 or off study	10 mL	sodium heparin tube
	7 mL	lithium heparin tube
	21 mL (three 7 mL tubes)	EDTA tube
	7mL	Blood (clot) tube

#### 8.1.1 Measurement of Antigen-Specific T-Cell Functions

Peripheral blood samples will be collected in EDTA vacutainer tubes prior to vaccination, one week after the third immunization, and one week following final PROSTVAC administration. Red blood cells will be lysed with ACK buffer for isolation of peripheral blood leukocytes (PBL). PBLs will be frozen in 90% FBS/10% DMSO using a controlled-rate freezer, and immediately stored in liquid nitrogen. Phenotypic characterization and detection of prostate specific antigen (PSA)-specific cytokine production from T cells within previously cryopreserved PBL will be performed

simultaneously. Briefly, PBLs will be stimulated at  $5 \times 10^6$  cells per test with peptide pools consisting of sequential 15mer peptides overlapping by 11 amino acids spanning the complete human PSA protein at 1 $\mu$ g/ml/peptide (Miltenyi), 1% DMSO negative control or polyclonal activation via 50 ng/mL phorbol myristate acetate (PMA) and 1  $\mu$ g/ml ionomycin for 6 hours. Brefeldin A (10 mg/mL) will be present for the last 5 hours. Samples will be labeled to exclude dead cells by incubation with amine reactive UV Live/Dead dye (Molecular Probes). Subsequently, T cell memory subsets will be phenotyped by staining for surface antigens using monoclonal antibodies specific for CD3, CD4, CD8, CD45RA, CD45RO, CCR7 and CD64L allowing for detection of naïve, stem cell memory, central memory, effector memory and terminally differentiated effector CD4 $^+$  and CD8 $^+$  T cells. Cells are then fixed and permeabilized by treatment with BD Cytofix/Cytoperm solution (BD Pharmingen) followed by labeling with monoclonal antibodies specific for IFN- $\gamma$ , IL-17A, IL-4, and IL-10 for 30 min at 4 $^{\circ}$ C in the presence of permeabilizing staining buffer to identify predominant TH1, TH17, TH2 and Treg cytokines, respectively. Cells will be collected immediately on a BD Fortessa X-20 flow cytometer capable of detection of up to 18 parameters (Beckman Dickinson). At least 300,000 events will be collected and data analyzed using FlowJo software. Values 3-fold higher than the DMSO background are scored as positive.

The proposed assay provides state-of-the-art immune monitoring of vaccine-induced PSA-specific immunity via multiparametric flow cytometry. Utilizing cutting-edge techniques, project investigators will simultaneously measure T cell memory status and determine the overall cytokine profile of vaccine-induced CD8 $^+$  and CD4 $^+$  T cell subsets. Detailed characterization of antitumor immunity will allow for the identification of immune correlates of protection from disease progression.

### 8.1.2 Measurement of Anti-Forssman Antibodies

Antibodies to heterophile antigens such as the glycolipid Forssman antigen commonly develop during certain infections. A recent report documented the appearance of antibodies to Forssman antigen during treatment of prostate cancer patients with PROSTVAC (32). Antibodies appeared in a high proportion of subjects (64%) and in high titer. Moreover, the appearance of anti-Forssman antibodies correlated with overall survival after vaccination, and the antibody titer was directly proportional to length of survival. The appearance of anti-Forssman antibodies during PROSTVAC therapy may represent a generalized activation of the immune system, or possibly antigen spreading. Project investigators will use a competitive immunoassay to detect anti-Forssman antibodies in serum from trial subjects before treatment, after the third injection, and after the final injection. Sheep RBCs will be purchased from commercial sources and used as a source of Forssman antigen. Washed RBCs will be incubated with serial dilutions of patient plasma, and with a FITC-labelled anti-Forssman monoclonal antibody. Binding of the labelled antibody will be measured by flow cytometry. Increasing amounts of anti-Forssman antibody in patient plasma will compete with the labelled antibody and reduce its binding, leading to decreased signal in the flow histogram. The amount of bound, labelled antibody will be quantified as the difference in maximum fluorescence intensity of the histogram curves, with irrelevant, isotype-matched antibody as a negative control, and labelled anti-Forssman antibody only (no competitor) as the positive controls. The result will be expressed as serum titer that inhibits binding of the labelled antibody probe by 90%.

### 8.1.3 Measurement of IgG Allotypes GM and KM

Polymorphic hereditary antigenic determinants present on IgG heavy chains are called GM allotypes (33, 34). These determinants are inherited as autosomal codominant genes according to Mendelian laws. They are encoded by three very closely linked genes—immunoglobulin heavy chain G1 (IGHG1), IGHG2, and IGHG3—on chromosome 14q32. GM alleles are expressed on the constant region of Y1, Y2, and Y3 chains. There are currently 18 serologically testable GM specificities—four on Y1 (1/a, 2/x, 3/f, 17/z), one on Y2 (23/n), and 13 on Y3 (5/b1, 6/c3, 10/b5, 11/b0, 13/b3, 14/b4, 15/s, 16/t, 21/g1, 24/c5, 26/u, 27/v, 28/g5). Linkage disequilibrium in the GM gene complex within a racial group is almost absolute and the determinants are transmitted as a group—haplotypes.

Polymorphic hereditary antigenic determinants present on Y-type light chains are called KM allotypes. Three alleles—KM 1, KM 1,2, and KM 3—segregate at the immunoglobulin Y constant (IGKC) locus on chromosome 2p12. KM 1 allele, without KM 2, is rare; 98% of the individuals positive for KM 1 are also positive for KM 2. Thus, positivity for KM 1 includes both KM 1 and KM 1,2 alleles (33,34).

Immunoglobulin GM genes are one of the most powerful tools for genetic characterization of human populations. For instance, unless there is genetic admixture, GM 3 is not found in African Americans; GM 6 is present only in people of African ancestry; GM 1 is polymorphic only in people of European ancestry. Their racially associated prevalence makes them especially suitable for investigations involving racial disparity in prostate cancer. Furthermore, these markers have been shown to contribute to both cellular and humoral immunity to several tumor-associated antigens in a racially restricted manner ((105-112)(113-115)). Thus, this project could potentially identify racially-specific genetic correlates of PROSTVAC vaccine efficacy. Immunoglobulin GM and KM genotyping may provide an import co-variant to measure along with stress responses. Because of almost absolute linkage disequilibrium between particular GM allotypes within a race, not all markers need to be typed to determine the major haplotypes segregating in a population.

### 8.1.4 TSC22D3/GILZ Genotyping

Psychological stress negatively influences cancer mortality, but the underlying molecular mechanisms are not known. Stress increases the secretion of glucocorticoids, which upregulates the transcriptional factor TSC22D3, also known as glucocorticoid-induced leucine zipper (GILZ). In mice, TSC22D3 acts as a “checkpoint” for anti-cancer immune responses. In humans, the gene encoding GILZ is located on human chromosome Xq22.3. Several single nucleotide polymorphisms (SNPs) have been identified in this gene. Using TaqMan® genotyping assays from Applied Biosystems Inc. and DNA from the trial participants, we will genotype for the following SNPs with appreciable minor allele frequencies:

rs12858266, rs17254207, rs3747406, rs6523975, rs6523976

These SNPs may influence the qualitative and quantitative expression of the TSC22D3/GILZ protein, resulting in interindividual differences in stress-induced

immunosuppression. We will determine whether these genetic markers are associated with allostatic load, stress reactivity, and the relapse risk in the vaccinees.

Thus, the SNPs to be genotyped in this project could be potential genetic modifiers of psychosocial stress and the outcome of immunotherapy in prostate cancer

### **8.1.5 GR Genotyping**

Trial participants will be genotyped for variants in the Bcl1 polymorphism (rs41423247) by collecting whole blood for genetic analysis. Blood samples will be stored at -80C for batch DNA extraction and genetic testing. Genomic DNA extraction from frozen blood will be done using the Purelink DNA extraction kit (QiaGen). Genotyping will be done using RFLP analysis and verified by sequencing at the MUSC Genomics Center.

## **8.2 FORMULIN FIXED PARAFFIN EMBEDDED TISSUE**

An attempt will be made to acquire FFPE tissue from all subjects, since study enrollment will be in close temporal proximity to the acquisition of the prostatectomy specimen. Should tissue be available for research, the study requires 5 thin (5 micron) sections on glass slides for H&E and IHC staining.

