**PROTOCOL SYNOPSIS**

Protocol Title:	A PHASE II TRIAL OF ADJUVANT PROSTVAC-V/F IN SUBJECTS AT HIGH RISK FOR RELAPSE AFTER RADICAL PROSTATECTOMY
Site Numbers & Names:	1. Hollings Cancer Center, Medical University of South Carolina, Charleston, SC 2. Ralph Johnson VA Medical Center, Charleston, SC
Research Hypothesis:	The hypothesis is that, in patients at high risk for relapse of PCa after radical prostatectomy, treatment with the PROSTVAC-V/F vaccine will improve Relapse Free Survival (RFS) compared with that expected for similar subjects given no adjuvant therapy.
Study Schema:	PROSTVAC-V $2 \times 10^8$ pfu subQ x 1, followed by PROSTVAC-F $1 \times 10^9$ pfu subQ x 6
Study Objectives:	
 
1. The primary endpoint is to determine the probability of RFS at 2 years after prostatectomy, and to compare it to RFS probability for historical control subjects without adjuvant treatment.
 
2. Secondary objectives are as follows:           
 
a) Compare observed RFSs to the predicted RFS values for the subjects as if they had received no adjuvant therapy. The predicted ("virtual") RFS for each subject will be calculated by standard algorithms.
 
b) Relate serial measurement of immunologic parameters, SNPs to RFS
 
c) Describe the toxicity for the treatment in this patient population
 
 
 

Study Design:	The study will be a Phase II, open-label trial conducted at two centers in the United States.
Accrual Goal:	30 evaluable subjects out of 33 total enrollees
Accrual Rate: (Number of subjects expected per month)	1.85 subjects per month x 18 months = 33 subjects. Assuming an in-evaluability rate of about 10%, this will give us 30 evaluable subjects.
Correlative Studies:	
 
1. Lymphocyte, monocytes subsets
 
2. Immunoglobulin, FcR SNPs
 
3. Plasma IL6, IL10, VEGF
 
4. Exon sequencing on tumor from FFPE tissue
 

Optional Study :	Potential patients will be approached to participate in an optional sub-study looking at sociobiological responses to stress in prostate cancer survivors.

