#### **3.2 SECONDARY OBJECTIVES**

There are four secondary objectives.

- To compare observed RFSs for the study population with the predicted RFSs for the study population. The predicted RFS values will be calculated from each patient's clinical and pathologic data by standard algorithms (Duke and CaPSURE). The observed and predicted RFSs will be presented as Kaplan-Meier plots and comparisons will be performed using the logrank test.
- To compare the observed RFS with the RFSs of a historical comparison group of MUSC prostatectomy patients. These patients will be matched to the experimental group for race, Gleason score, and pathological stage. The observed, historical RFSs will be presented as Kaplan-Meier plots and comparisons will be performed using the logrank test.
- To describe associations between the RFS values and various immunologic, genetic, and biochemical parameters on research blood and tissue specimens.
- To describe the toxicity of PROSTVAC-V/F in this patient population.

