### 7.1 THERAPEUTIC TRIAL PROCEDURES

A variety of clinical assessments are made during the screening period and while the subject is on study. These include the following. Specific details about the timing of these procedures can be found in the study calendar ([Appendix A](#)):

- Patients will be given instructions on how to care for the injection site after each injection of PROSTVAC-V and PROSTVAC-F.
- History and physical examination. The history includes a review of the prostatectomy pathology report to ensure that it includes the following information: date of surgery, subject's age at surgery, pre-op PSA, Gleason score, margin status, extraprostatic extent, seminal vesicle status, lymph node status. A measurement of the PSA at 45 or more days after surgery is also necessary, if the post-prostatectomy PSA nadir is not < 0.2 ng/mL before then.
- CBCD
- CMP (sodium, potassium, chloride, bicarbonate, BUN, creatinine, glucose, albumin, alkaline phosphatase, AST, ALT, calcium);
- Lipid Panel (total cholesterol, HDL cholesterol, triglycerides, LDL cholesterol, non-HDL cholesterol). Lipid panel will only be done at baseline and requires patients to be fasting. If a fasting blood draw cannot be done at screening (prior to registration), it may be done on day 1 prior to agent administration.
- PSA
- Testosterone
- C-reactive protein
- HIV, Hep B and Hep C serology screening, unless known negative within previous 2 years prior to registration.

- Scans: Technetium bone scan (but not F-fluoride PET scan); CT scan of abdomen, pelvis (a Prostascint scan or MRI of abdomen, pelvis can be substituted). Scans can be done up to 26 weeks prior to start of treatment.

Correlative research will include the following:

- FACT-P, AUA SS, and SHIM quality of life questionnaires
- Collection of blood for research (refer to Section 8):
  - 10 mL blood in a sodium heparin tube
  - 7 mL blood in a lithium heparin tube
  - 21 mL blood in a EDTA tube
  - 7 mL blood in a serum (clot) tube
- FFPE tissue, if available: 5 thick (20 micron) sections on plastic slides for genomic analysis, plus 5 additional thin (5 micron) sections

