### 10.2.3 Correlative Laboratory Studies

Biochemical and genomic measurements will be summarized both graphically and numerically using descriptive statistics. Transformations will be performed based on the observed distribution of the endpoints. Cox regression will be used to estimate hazard ratios measuring the association between these measures and RFS. 95% confidence will be estimated for the hazard ratios as appropriate.

For the amount of antibody forcement antigen, graphical displays such as scatterplots of optical density of particular color and dilution will be made for pre- and post-vaccination. To investigate if the distributions of pre- and post-vaccination are different, Kolmogorov-Smirnov test will be performed. The reverse sigmoidal curves will fit to estimate model parameters such as slope and 50% of maximum effect for the antibody measurement. Depending on the curve results, different percentages of maximum effect (e.g., 65-75%) will be investigated as well. Moreover, those interest of immune parameters will be compared between pre- and post-vaccination. The

difference of the immune parameters will be used for measuring the association between these measures and time to relapse/stress.

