## 10.5 ADDITIONAL ANALYSES

Demographic and clinical parameters will be tabulated. Critical parameters to be recorded include age at time of surgery, date of surgery, race, primary Gleason score, secondary Gleason score, pathologic stage, surgical margin status, extraprostatic extension status, seminal vesicle status, lymph node status, pre-operative PSA level, post-operative PSA level (> 6 wks after surgery). Formalin-fixed paraffin-embedded tissue from the prostatectomy specimen will be archived for future “omic” analyses to correlate with RFS.

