- j. If available: Send 5 thin (5 micron) sections on glass for H+E and IHC staining. These can be sent at any time after consent has been signed.
- k. Lipid panel requires patients to be fasting and can be done any time after informed consent is signed and prior to day 1 agent administration.
- l. HIV, Hep B and Hep C serology screening, unless known negative within previous 2 years prior to registration.
- m. PSA confirming eligibility can be done outside of the 30 day window. However, if PSA confirming eligibility was done greater than 30 days prior to day 1, it should be repeated prior to day 1 agent administration to ensure PSA is < 0.2ng/mL
- n. Day 1 assessments completed within 24 hours of screening assessments do not need to be repeated.
- o. Interim medical history includes any changes to the patient's medical history and/or any clinical changes since the previous clinic visit.
- p. For non-local patients in follow up, all attempts should be made to have subject return to the clinic for all follow up visits, but specifically day 225 and day 703. However, clinical care procedures (PSA, CMP, CBCD, focused physical exam and interim medical history – to include AE assessment and conmed assessment) may be done locally and the records provided. At a minimum, a PSA must be done and results provided to the study team. If a clinic visit is not done during follow up, the study team may conduct a phone interview (using the phone contact guide, Appendix D) in lieu of an clinic visit to assess adverse events, current cancer therapy and PSA level. Quality of life surveys may also be conducted over the phone by the study team if the subject does not return to clinic.
- q. Questionnaires may be mailed to the subject in pre-metered envelope if they are unable to come into the clinic to complete them (ie: due to COVID19 travel restrictions). The subject will complete the questionnaires at home and then mail the completed questionnaires back to the main site in the provided envelope.

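### The FFPE instructions conflict: Section 7.1 asks for thick tumour sections for genomic analysis, while Section 8.2 and Appendix A note j ask only for thin sections for staining

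*Combined protocol and SAP*

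**What the plan says.** Five places in the combined protocol and SAP bear on what tumour tissue is collected, and two more say what it is for.

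- Synopsis, Correlative Studies, item 4: "Exon sequencing on tumor from FFPE tissue".
- Section 7.1, correlative research list, where tissue is available: "5 thick (20 micron) sections on plastic slides for genomic analysis, plus 5 additional thin (5 micron) sections".
- Section 8.2, where tissue is available: "the study requires 5 thin (5 micron) sections on glass slides for H&E and IHC staining". No thick sections and no genomic use are mentioned.
- Appendix A, note j: "If available: Send 5 thin (5 micron) sections on glass for H+E and IHC staining". The note adds that sections may be sent at any time once consent is signed.
- Section 10.5: FFPE "tissue from the prostatectomy specimen will be archived for future" omics work to be related to RFS. No number, thickness or format is given.
- Section 3.2, third objective: to describe associations of RFS with "various immunologic, genetic, and biochemical parameters on research blood and tissue specimens".
- Section 10.2.3: "Biochemical and genomic measurements will be summarized both graphically and numerically using descriptive statistics", followed by Cox regression of RFS on these measures.

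**The concern.** A listed assay needs a specimen, and only one of the three collection instructions supplies it. Sections 8.2 and Appendix A are natural places for a coordinator to look: 8.2 is the FFPE section, and the opening of Section 7 sends readers to Appendix A for the schedule of procedures. Someone using either would have no prompt to cut or ship the thick sections.

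What is at stake is the tumour-genomic part of the third secondary objective. Tissue is collected only where available and the trial is small, so a further loss caused by wording alone is worth avoiding. The opposite error is also possible. If sequencing has been dropped, the synopsis and 7.1 are out of date, and sites following 7.1 would cut tissue that no assay uses.

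**Working it through.** The plan states no figure on this point to reproduce. The check is a comparison of the texts with two small pieces of arithmetic.

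**Step 1. The three collection instructions side by side**

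| Source | 20-micron sections | 5-micron sections | Stated use |
|---|---|---|---|
| Section 7.1 | 5, on plastic slides | 5 | thick: genomic analysis; thin: not stated |
| Section 8.2 | none mentioned | 5, on glass | H&E and IHC |
| Appendix A note j | none mentioned | 5, on glass | H&E and IHC |

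Sections designated for genomic analysis: 5 of 5 under 7.1, and 0 of 5 under 8.2 or note j.

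In total thickness, 7.1 gives 5 × 20 + 5 × 5 = 125 microns, of which 5 × 20 = 100 are for genomic work. Section 8.2 and note j give 5 × 5 = 25 microns, of which 0 are for genomic work. The documents set no DNA yield requirement, so the ratio 25/125 = 20% only restates the two lists and does not measure analytic loss.

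**Step 2. Does another passage fill the gap?**

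- Section 10.5 archives prostatectomy tissue for future omics work, but has no collection instruction of its own. It does not say that thick sections are sent.
- The genotyping in Sections 8.1.3 to 8.1.5 sits under research blood collections and uses blood or participant DNA. It does not supply tumour tissue.
- Section 8 contains no description of a tumour-sequencing assay, so it does not show whether sequencing is still intended.
- All these passages are current text, and none is a record of superseded wording.

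**Step 3. How much information does the affected analysis have?**

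Inputs: 30 evaluable men, and two-year RFS of 0.60 (null) or 0.78 (alternative), from the synopsis and Section 10.1. Expected RFS events by two years = n × (1 − RFS).

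- At 0.78: 30 × (1 − 0.78) = 6.6, about 7.
- At 0.60: 30 × (1 − 0.60) = 12.

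A Cox model of RFS on tumour-genomic measures would therefore have about 7 to 12 events even with tissue from every man. With tissue only where available, it would have fewer.

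**The case against.** The strongest reply is that this is a wording mismatch with limited consequences. Several parts of that reply stand.

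- **The lists are not mutually exclusive.** Neither 8.2 nor note j contains the word only, and nothing says that they override the quantities in 7.1. A site meeting the whole protocol would send both sets. This is correct, so the failure is conditional on a site working from 8.2 or note j alone.
- **Tumour tissue is still collected.** A reader might infer that the trial would hold no tumour tissue. The documents do not support that: five thin sections from the prostatectomy specimen are requested, and 10.5 plans an archive. What is missing is tissue designated for sequencing.
- **The loss may be recoverable.** Note j allows sections to be sent at any time after consent, and nothing shows that a missed request could not be made good.
- **The objective is descriptive.** It carries no hypothesis test, power or error rate, and the blood-based genotyping serves part of its genetic component.

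Two further inferences go beyond the documents. One is that any loss would remove most of the information. Step 3 gives an event count, not a measure of information lost, so all that follows is that already sparse information is reduced. The other is that missingness would differ between the two sites. Nothing shows that the sites work from different sections, and one unit coordinates both.

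None of this removes the conflict. Two of three instructions omit the material that a listed assay needs, and no passage says which list governs.

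**Conclusion.** The FFPE collection instructions contradict each other and should be reconciled. A site following 8.2 or note j as written would send 0 of the 5 thick sections, which would reduce or remove the tumour-genomic part of a descriptive secondary correlative with about 7 to 12 expected events among 30 men. The primary endpoint, sample size, error rates and safety monitoring are untouched.

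The size rests on three assumptions: that sequencing is still intended, that some site works from 8.2 or note j without 7.1, and that 30 evaluable men is the current target. Section 4.1 still gives forty. On that figure the event range would be 40 × 0.22 = 8.8 to 40 × 0.40 = 16, which leaves the conclusion unchanged.

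The documents do not show whether 7.1 and the synopsis are out of date or whether 8.2 and note j are incomplete. The conflict needs settling in either case.

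**What to change.** The sponsor should first decide whether tumour exon sequencing is still planned, and then make one set of edits.

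- **If it is planned:** put the 7.1 list (five 20-micron sections for genomic analysis plus five 5-micron sections) into 8.2 and Appendix A note j. Request the thick sections for men already enrolled where tissue is available.
- **If it has been dropped:** remove exon sequencing from the synopsis and the thick sections from 7.1.

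Under either choice, leave the Section 10.5 archive in place and add what tissue supplies it. That section does not mention sequencing, and dropping the assay is no reason to delete a separate plan.

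The cost is wording in two places plus a clarifying phrase in 10.5. Under the first option there is also the work of requesting and cutting further sections from prostatectomy tissue. The documents do not say how much tissue remains accessible, so the number of men for whom this can be done is unknown. Neither option changes treatment or patient visits.
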